5.3.1.2.2. Tipping Point Analysis

The response status (yes/no) of a participant with missing data is multiply imputed by randomly drawing from a Bernoulli distribution with changing underlying probability independently for each treatment arm. The detailed steps are described below.

- Step 1: Assume a response proportion p_0 for all participants with missing data in the placebo group and a response proportion p_1 for all participants with missing data in the etrasimod group.
- Step 2: Impute the missing response for each participant from the Bernoulli distribution with response probability p₀ for placebo group and response probability p₁ for etrasimod group, independently. Combine with the participants with

nonmissing response to have a complete dataset. The random seed **8238946** will be used.

- Step 3: Repeat Step 2 and generate N (eg, N=40) complete datasets.
- Step 4: For each complete dataset, obtain the estimated common risk difference and its standard error using the weighted MH weighted method, stratified by (a) naïve to biologic or JAK inhibitor therapy at study entry (yes or no) and (b) baseline corticosteroid use (yes or no).
- Step 5: Combine and obtain the final estimated common risk difference, its 95% 2-sided confidence intervals and test p-values based on the Rubin's rule and SAS PROC MIANALYZE
- Step 6: For each combination of (p₀, p₁) over a plausible region (say, p₀ from to 0.3, and p₁ from 0.0 to 0.5), repeat Step 1 through Step 5 to produce a significance tipping point map to help the determination of the tipping point boundary.

5.3.1.2.3. Copy Reference (CR) Multiple Imputation Under MNAR Assumption

Missing data will also be explored assuming an MNAR approach. MNAR assumes the missing values depend on unobserved outcomes even after accounting for the observed data. Therefore, participants cannot be modelled based on participants with observed data, and more assumptions are needed. Copy Reference approach (Carpenter et al, 2013) will be used. It is a type of missing data handling approach, assuming MNAR, where each missing value of MMS subscores for participants in the treatment group will be imputed using observed MMS subscores in the placebo group, and missing values of MMS subscores for participants in the placebo group will be imputed under the MAR approach. Once the missing MMS subscores are imputed, all binary efficacy endpoints (based on MMS) will be derived based on observed and imputed MMS subscores and analyzed using the same method described in Section 5.2.1 for each imputed dataset. Then the results will be combined using multiple imputation methodology based on the Rubin's rule. The random seed 8238946 will be used.

Step 1

Step 1 (a)

Intermittent missing data (before discontinuation from study) at each scheduled visit will be imputed, separately for each treatment group, under the MAR assumption using a multivariate normal imputation model and the Markov Chain Monte Carlo (MCMC) method with multiple chains. The number of imputations will be 40. The resulting data will have a monotone missing data pattern. The imputed data will be used together with the observed data to impute post discontinuation missing values.

Step 1 (b)

Only after Step 1a is completed, the remaining monotone missing data after discontinuation will be imputed using the FCS predictive mean matching method based on data from the

placebo group only. The RB, SF, ES, and PGA subscores, stratification variables, a binary variable indicating if a participant is a treatment failure, and biomarker measurements (ALC, FCP, hs-CRP, log-transformed) at each planned visit will be included in the imputation model.

Step 2

Same as Step 2 described in Section 5.3.1.2.1 above.

Step 3

Same as Step 3 described in Section 5.3.1.2.1 above.

Step 4

Same as Step 4 described in Section 5.3.1.2.1 above.

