2.2.3. Primary Estimand (Estimand 1)

The primary estimand of this study is a composite estimand, which estimates the effect of randomized treatment accounting for treatment adherence and response.

- Treatment: Etrasimod 2 mg vs Placebo
- Population: Participants with mildly to moderately active UC as defined in 2022
 FDA Draft Guidance; Ulcerative Colitis: Developing Drugs for Treatment (Section 8 References)
- Variable: primary efficacy endpoint of clinical remission at week 52 and all binary efficacy endpoints as described in Sections 3.1, 3.2.1 and 3.4.1
- Intercurrent events: the following intercurrent events are defined:
 - 1) Discontinue the study treatment during the double blind treatment period for any reasons
 - 2) Initiate a rescue medication for UC (Section 9.3)
 - 3) Have an increase in dose over baseline levels in their existing UC medication following the rules in Section 9.3

4) Have a rescue non-drug treatment (eg, colectomy, ileostomy, or sigmoidectomy) during the study (Section 9.3)

Participants having any of the intercurrent events as defined in 1) - 4) above will be considered as nonresponders, that is, have a known outcome of nonresponse at applicable timepoints. Missing measurements due to other reasons will be treated as missing. The method of dealing with missing data is presented in Section 5.3

 Population-level summary: Proportion of participants who are responders in each treatment group and differences in proportions of responders between Etrasimod 2 mg group and placebo group.

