5.3.1.1. Primary Missing Data Handling Method

For binary efficacy endpoints, participants having any of intercurrent events 1) discontinue the study treatment during the double blind treatment period for any reasons, or 2) initiate a rescue medication for UC, or 3) have an increase in dose over Baseline levels in their existing UC medication, or 4) have a rescue non-drug treatment (eg, colectomy, ileostomy, or sigmoidectomy) during the study will be considered as nonresponders, that is, have a known outcome of nonresponse at any applicable timepoints.

For primary analysis, all participants with missing data for other reasons will be treated as nonresponders. That is, all missing data will be treated as nonresponse regardless of reasons.

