5.3.1.2.4. Hybrid Imputation For Missing Data Due to COVID-19 Pandemic and Ukraine war

The COVID-19 pandemic and Ukraine war introduces unexpected and unknown impact on the clinical study due to unforeseen intercurrent events. As a sensitivity analysis for primary and key secondary efficacy endpoints, missing endoscopy data will be handled using a hybrid approach combining nonresponder Imputation (NRI) and multiple imputation, where participants with missing endoscopy data due to COVID-19 pandemic and Ukraine war will be imputed using multiple imputation method under a MAR assumption, as described in Section 5.3.1.2.1. The random seed **8238946** will be used. Missing data for any other reason will be considered a nonresponse.

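### Copy Reference Step 1(b) imputes outcomes after discontinuation for participants whom the primary estimand already defines as nonresponders, so the step either changes the estimand or has no effect

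*SAP*

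**What the plan says.** **Estimand.** SAP 2.2.3 lists as intercurrent event 1 "Discontinue the study treatment during the double blind treatment period for any reasons". It continues: "Participants having any of the intercurrent events as defined in 1) - 4) above will be considered as nonresponders". Only what is left counts as missing: "Missing measurements due to other reasons will be treated as missing". SAP 5.3.1.1 repeats the rule and adds, for the remainder, "For primary analysis, all participants with missing data for other reasons will be treated as nonresponders".

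**Copy Reference.** SAP 5.3.1.2.3 has two imputation steps. Step 1(a): "Intermittent missing data (before discontinuation from study) at each scheduled visit will be imputed, separately for each treatment group, under the MAR assumption". Step 1(b): "the remaining monotone missing data after discontinuation will be imputed using the FCS predictive mean matching method", fitted to the placebo group only. The section then says "all binary efficacy endpoints (based on MMS) will be derived based on observed and imputed MMS subscores". Its Step 2 refers back to Step 2 of 5.3.1.2.1, which classifies each participant as responder or nonresponder in each imputed dataset. Neither place says that a participant with an intercurrent event keeps the nonresponse.

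**Hybrid.** Under SAP 5.3.1.2.4, "participants with missing endoscopy data due to COVID-19 pandemic and Ukraine war will be imputed using multiple imputation method under a MAR assumption". Data missing for any other reason count as nonresponse. Discontinuation is not mentioned.

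**The concern.** A sensitivity analysis of Estimand 1 should vary the assumption about data that are missing under Estimand 1 and leave the rest alone. Step 1(b) is written for participants whose outcome is not missing under that estimand. If CR moved the treatment difference, a reader could not tell whether the missing-data assumption or a change of estimand was responsible. If CR agreed with the primary result because Step 1(b) did nothing, the agreement would be reported as robustness to an MNAR mechanism that was never exercised. SAP Table 6 plans CR for the primary endpoint and every key secondary endpoint, and two programmers could follow the text to different results.

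**Working it through.** **Who falls under Step 1(b).** Leaving the study before Week 52 entails stopping double-blind treatment. After stopping, protocol 5.1 and 9.5 schedule only an early-termination visit and the 2- and 4-week follow-up visits, so an early leaver will generally have no Week 52 endoscopy. These are the participants with monotone missing data after discontinuation. All of them have intercurrent event 1, hence a known Week 52 nonresponse.

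**The two readings.**

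- *Imputed scores decide.* This follows the derivation sentence of 5.3.1.2.3 and Step 2. Some defined nonresponders are scored as remitters, so CR no longer targets Estimand 1.
- *The estimand rule decides.* Step 1(b) changes no Week 52 outcome. What still matters is Step 1(a), which is MAR within each arm. No placebo-based imputation reaches the endpoint.

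The treatment-failure indicator in Step 1(b) does not settle the matter: it is a covariate in the imputation model, not a scoring rule.

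**Probable origin.** Protocol 10.4 treated discontinuations unrelated to UC as missing data, so CR had participants to impute. The SAP version history lists the any-reason rule against 2.2.3, 2.2.4 and 5.3.1.1; for the imputation methods it lists random seeds and the Ukraine war. That 5.3.1.2.3 was not revisited is an inference.

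**Planning figures (background only).** SAP 2.3 assumes 34% v 14% with 122 and 61 participants, two-sided 0.05. Exact enumeration of Fisher's test gives power 83.8%, consistent with the stated minimum of 80%. The normal approximation with unpooled variance gives 89.95%, in effect the stated 90%; the pooled form gives 84.6%.

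**Size under the first reading.** No discontinuation rate is given, so the rates below are assumptions. Take 34% and 14% as the rates with every discontinuer counted as a nonresponder. Let d_E and d_P be the proportions discontinuing, and let Step 1(b) give discontinuers the placebo completer rate q = 0.14 / (1 − d_P). Then:

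- etrasimod becomes 0.34 + d_E × q
- placebo becomes 0.14 + d_P × q
- the difference becomes 0.20 + (d_E − d_P) × q
- expected nonresponders turned into responders: 122 × d_E × q and 61 × d_P × q

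| d_E / d_P | q | Etrasimod | Placebo | Difference (points) | Turned, etrasimod / placebo |
|---|---|---|---|---|---|
| 10% / 10% | 0.156 | 35.6% | 15.6% | 20.0 | 1.9 / 0.9 |
| 20% / 20% | 0.175 | 37.5% | 17.5% | 20.0 | 4.3 / 2.1 |
| 10% / 30% | 0.200 | 36.0% | 20.0% | 16.0 | 2.4 / 3.7 |
| 10% / 40% | 0.233 | 36.3% | 23.3% | 13.0 | 2.8 / 5.7 |
| 30% / 10% | 0.156 | 38.7% | 15.6% | 23.1 | 5.7 / 0.9 |

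Worked row, 10% / 30%: q = 0.14 / 0.70 = 0.20; etrasimod 0.34 + 0.10 × 0.20 = 0.36; placebo 0.14 + 0.30 × 0.20 = 0.20; difference 0.16.

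**Size under the second reading.** Step 1(b) contributes zero change.

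**The other methods.** The MAR multiple imputation (5.3.1.2.1) and the tipping-point analysis (5.3.1.2.2) also do not say that the intercurrent-event rule comes first. In the hybrid the conflict is confined to a participant who stopped treatment because of COVID-19 or the war: 2.2.3 makes that a nonresponse, while 5.3.1.2.4 can be read as imputing the missing endoscopy.

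**The case against.** The best defence is that the SAP already contains the rule. Section 5.3.1 introduces the primary and sensitivity methods as applying to participants with a missing binary outcome, and 2.2.3, which is not confined to the primary analysis, says that discontinuers have a known one. Read together, discontinuers are outside the pool to be imputed. This is a reasonable reading, but it leaves Step 1(b) with nothing to do, and the explicit instruction to impute after discontinuation still stands against it.

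It can also be said that protocol 10.4 itself planned placebo-based imputation after discontinuation, so keeping it may be deliberate. If so, the analysis addresses a different estimand and should be labelled accordingly.

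Three stronger inferences are tempting, and the documents do not support them:

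- *That the hybrid analysis also imputes people who left.* Its text does not say so. It has a valid target: participants still on treatment whose endoscopy was missed. The widened windows in SAP 9.1.4 show that affected assessments were anticipated.
- *That CR imputes no one, or that robustness is not examined at all.* Step 1(a), the MAR multiple imputation, the tipping-point analysis and the hybrid all keep real targets. The tipping-point analysis varies the response probability separately by arm, so departures from MAR are still explored.
- *That CR will shrink the treatment difference.* The direction depends on which arm has more dropout. Step 1(b) also conditions on each participant's own scores and biomarkers, so those who left with active disease may be imputed below the completer rate used above.

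**Conclusion.** The conflict is real and lies in CR Step 1(b). Under one reading the step credits defined nonresponders with remission; under the other it is inert, and an analysis labelled MNAR rests on within-arm MAR imputation. The primary analysis is untouched, because all missing data there are nonresponse.

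Under the first reading the illustrated difference runs from 13.0 to 23.1 points against 20, with no change when dropout is equal. These values rest on assumed discontinuation rates, on 34% and 14% being rates with discontinuers counted as failures, and on a flat placebo completer rate for every discontinuer. They show that the effect can go either way; they do not predict it.

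For the MAR, tipping-point and hybrid methods the defect is narrower: no stated precedence, which for the hybrid matters only for treatment stopped because of COVID-19 or the war. The plan should be amended before unblinding.

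**What to change.** 1. Add a precedence rule at the head of SAP 5.3.1.2: in every sensitivity analysis of Estimand 1 (MAR multiple imputation, tipping point, CR, hybrid), participants with intercurrent events 1) to 4) are scored as nonresponders at the applicable timepoints whatever their imputed values. Say that this includes participants who stopped treatment because of COVID-19 or the war.
2. Redefine CR. The precedence rule alone would leave Step 1(b) inert. Replace its trigger, so that placebo-based imputation applies to outcomes missing without a prior intercurrent event, and state which gaps remain in Step 1(a).
3. If imputation after discontinuation is still wanted, keep it as a supplementary analysis with its own stated estimand, in which discontinuation is not treated as failure.

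The cost is SAP wording, a flag applied at scoring and a revised CR program. The downside is that few participants may remain to impute, so the sensitivity results will sit closer to the primary result.

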5.3.1.2.4. Hybrid Imputation For Missing Data Due to COVID-19 Pandemic and Ukraine war

The COVID-19 pandemic and Ukraine war introduces unexpected and unknown impact on the clinical study due to unforeseen intercurrent events. As a sensitivity analysis for primary and key secondary efficacy endpoints, missing endoscopy data will be handled using a hybrid approach combining nonresponder Imputation (NRI) and multiple imputation, where participants with missing endoscopy data due to COVID-19 pandemic and Ukraine war will be imputed using multiple imputation method under a MAR assumption, as described in Section 5.3.1.2.1. The random seed **8238946** will be used. Missing data for any other reason will be considered a nonresponse.

5.3.2. Continuous Non-Cardiac Endpoints

For all non-cardiac continuous (i.e., exploratory efficacy endpoints, HRQoL endpoints and efficacy-related biomarker endpoints) endpoints measured longitudinally, missing values post baseline will not be imputed explicitly. For such endpoints, assuming that the missing data mechanism is missing at random (MAR), the data will be analyzed based on a linear mixed-effect model for these continuous endpoints (Section 5.2.2)

5.3.3. Cardiac Endpoints

For all cardiac endpoints, missing values will not be imputed explicitly.

5.4. Supplementary Analyses for Primary and Key Secondary Efficacy Endpoints

For primary endpoint analysis, the primary model as described in Section 5.2.1 will be repeated using the mPAS (with data as observed) as a supplementary analysis. For key secondary efficacy endpoint analyses, the primary model as described in Section 5.2.1 will be repeated using the mPAS (with data as observed) as supplementary analyses.

6. ANALYSES AND SUMMARIES

6.1. Summaries and Analyses for Efficacy, HRQoL and Efficacy-Related Biomarker Endpoints

The detailed summaries of analyzing the efficacy, HRQoL and efficacy-related biomarker endpoints listed in Sections 3.1, 3.2.1, 3.4.1, 3.4.2 and 3.4.3 are provided in Table 6 and Table 7 below. All outputs will be based on the PAS, unless otherwise specified.

Table 6. Planned Analyses for Primary and Key Secondary Efficacy Endpoints

Endpoint	Main Analysis	Main Missing Data Handling	Sensitivity Missing Data Handling	Supplementary Analyses
Primary endpoint		1	, 9	
Clinical remission at Week 52	MH weighted method (Section 5.2.1) based on PAS	NRI	MI assuming MAR, Tipping point analysis, CR MI assuming MNAR, hybrid imputation	mPAS (observed data)
Key secondary efficacy endpoint		1	1	l
Endoscopic improvement at Week 52	Same as primary endpoint	Same as primary endpoint	Same as primary endpoint	Same as primary endpoint
12-week corticosteroid-free clinical remission at Week 52	Same as primary endpoint	Same as primary endpoint	Same as primary endpoint	Same as primary endpoint
Clinical remission at Week 12	Same as primary endpoint	Same as primary endpoint	Same as primary endpoint	Same as primary endpoint
Endoscopic improvement at Week 12	Same as primary endpoint	Same as primary endpoint	Same as primary endpoint	Same as primary endpoint
Sustained clinical remission (clinical remission at both Week 12 and Week 52)	Same as primary endpoint	Same as primary endpoint	Same as primary endpoint	Same as primary endpoint
Histologic- Endoscopic Mucosal Improvement at Week 52	Same as primary endpoint	Same as primary endpoint	Same as primary endpoint	Same as primary endpoint

Table 6. Planned Analyses for Primary and Key Secondary Efficacy Endpoints

Endpoint	Main Analysis	Main Missing Data Handling	Sensitivity Missing Data Handling	Supplementary Analyses
Complete symptomatic remission at Week 52	Same as primary endpoint	Same as primary endpoint	Same as primary endpoint	Same as primary endpoint
Complete symptomatic remission at Week 12	Same as primary endpoint	Same as primary endpoint	Same as primary endpoint	Same as primary endpoint

Table 7. Planned Analyses for Other Secondary Efficacy, Exploratory Efficacy, HRQoL and Efficacy-Related Biomarker Endpoints

Endpoint	Main Analysis	Main Missing Data Handling	Sensitivity Missing Data Handling	Supplementary Analyses
Other secondary efficacy endpoints (Section 3.2.1)	Same as primary endpoint	Same as primary endpoint	N/A	N/A
Exploratory efficacy endpoints: binary endpoints (Section 3.4.1)	Same as primary endpoint	Same as primary endpoint	N/A	N/A
Exploratory efficacy endpoints: continuous endpoints (Section 3.4.1)	linear mixed-effect model based on PAS (Section 5.2.2)	Data will not be imputed explicitly, assuming MAR (Section 5.3.2)	N/A	N/A
HRQoL endpoints (Section 3.4.2)	Same as continuous exploratory efficacy endpoint	Same as continuous exploratory efficacy endpoint	N/A	N/A
Efficacy-related biomarker endpoints (Section 3.4.3)	Same as continuous exploratory efficacy endpoint except that the analysis for lymphocyte counts will be based on Safety Set, not PAS	Same as continuous exploratory efficacy endpoint	N/A	N/A

For continuous endpoint, line plots over time for LS mean and SE by treatment will be provided if deemed appropriate.

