10.10.2. Health-Related Quality of Life

- Scores and change from baseline at Weeks 12, 32 (UC-PRO only), and 52 in the following:
 - Two UC-PRO modules:
 - UC-PRO/SS and
 - UC-PRO Systemic Symptoms
 - FACIT-F
 - WPAI-UC
 - Urgency NRS
 - IBDQ
 - SF-36
 - PGIC
- The proportion of subjects with UC-related hospitalizations
- The proportion of subjects requiring UC-related surgeries, including colectomy

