16. APPENDICES

APPENDIX 1: SCHEDULE OF ASSESSMENTS

Table 6: Schedule of Assessments

Evaluation	Screening		12-Week Treatment Perioda					40-Week Treatment Period ^a						
	-28 to -1	W0/ D1	W2/ D15 ± 3	W4/ D29 ± 3	W8/ D57 ± 3	W12/ D85 ± 3 ^b	W16/ D113 ± 7	W24/ D169 ± 7	W32/ D225 ± 7	W40/ D281 ± 7 (virtual)	W48/ D337 ± 7	W52/D 365/ ET ± 7 ^b	2W F/U ± 3°	4W F/U ± 3°
Informed consent	X													
Inclusion/exclusion criteria	X	X												
Demographics	X													
Medical and social historyd	X													
Ulcerative colitis history	X													
Chest X-raye	X													
Tuberculosis test ^f	X											X		
Tuberculosis questionnaire ^f	X	X	X	X	X	X	X	X	X	X	X	X	X	X
Virology screen (HIV, HBV, HCV) ^g	Х													
Randomization		X												
eDiary instructionh	X													
eDiary review		X	X	X	X	X	X	X	X	X	X	X		
PGAi		X				X						X		
MMS/TMS ^j		X				X						X		
Stool frequency and rectal bleeding subscores ^k		Х	X	X	X	X	X	Х	Х	Х	X	X		

Evaluation	Screening	12-Week Treatment Perioda 40-Week Treatment Peri			iod ^a									
	−28 to −1	W0/ D1	W2/ D15 ± 3	W4/ D29 ± 3	W8/ D57 ± 3	W12/ D85 ± 3 ^b	W16/ D113 ± 7	W24/ D169 ± 7	W32/ D225 ± 7	W40/ D281 ± 7 (virtual)	W48/ D337 ± 7	W52/D 365/ ET ± 7 ^b	2W F/U ± 3c	4W F/U ± 3°
IBDQ, UC-PRO ¹ , SF-36, WPAI-UC, FACIT-F, urgency NRS, and PGIC		X				Х			Xm			X		
Adverse event assessment	+												-	
Vital signs ⁿ	X ⁿ	Xn,o	X	X	X	X	X	X	X		X	X	X	X
12-lead ECG ^p	$\mathbf{X}^{\mathbf{q}}$	$\mathbf{X}^{\mathbf{p},\mathbf{q}}$				X						X		
Holter monitor ^r		X												
Physical examinations	X	X	X	X	X	X	X	X	X		X	X	X	X
Extraintestinal manifestations ^t	X					X						X	X	X
Pulmonary function test ^u	Xv					X			X			X	X	
Ophthalmoscopy with OCTw	X					X						X	X	
Urine drug screen ^x	X													
Pregnancy test ^y	X	X		X	X	X	X	X	X	X	X	X		X
CBC with differential and platelets ^z	X	X	X	X	X	X	X	X	X		X	X	X	X
CCI	X	X	X	X	X	X	X	X	X		X	X	X	X
Laboratory tests including hs-CRP ^{aa}	X	X	X	X	X	X	X	X	X		X	X	X	
Stool sample/fecal calprotectin ^{bb}	X		X	X	X	X		X				X		
CCI	X					X						X		
Endoscopy and biopsy (histologic indices) ^{cc}	X					X						X		

090177e1a2002994\Approved\Approved On: 23-Oct-2024 03:11 (GMT)

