2.2.4. Secondary Estimand (Estimand 2)

The secondary estimand of this study is a hypothetical estimand, which estimates the effect of randomized treatment as if all participants maintain their randomized treatment.

- Treatment: Etrasimod 2 mg vs Placebo
- Population: Participants with mildly to moderately active Ulcerative Colitis (UC) as described in 2022 FDA Draft Guidance; Ulcerative Colitis: Developing Drugs for Treatment.
- Variable: change from baseline in MMS and other continuous variables for exploratory efficacy endpoints, HRQoL endpoints and efficacy-related biomarker endpoints as described in Sections 3.4.1, 3.4.2 and 3.4.3, respectively.
- Intercurrent events: The following intercurrent events are defined:
 - 1) Discontinue the study treatment during the double blind treatment period for any reasons
 - 2) Initiate a rescue medication for UC (Section 9.3)
 - 3) Have an increase in dose over baseline levels in their existing UC medication following the rules in Section 9.3.
 - 4) Have a rescue non-drug treatment (eg, colectomy, ileostomy, or sigmoidectomy) during the study (Section 9.3)

For participants having any of the intercurrent events as defined in 1) - 4) above, their data collected up to the intercurrent events will be used for analysis.

• Population-level summary: Least-squares mean (LSM) (Section 5.2.2) in each treatment group and differences in LSMs between Etrasimod 2 mg group and placebo group (Section 5.2.2).

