 items), and social function (5 items). Responses are graded on a 7-point
 Likert scale where 7 denotes "not a problem at all" and 1 denotes "a very
 severe problem". Scores range from 32 to 224, a higher score indicates better
 quality of life. Details about scoring rules for IBDQ total score and 4 domain
 subscores can be found in Section 9.2.2.
- Medical Outcomes Study 36-Item Short Form Health Survey, version 2 physical and mental component and domain scores (SF-36). The 36-Item Short Form Health Survey (SF-36) is a 36-item, participant-reported survey of participant health. The SF-36 consists of 36 questions measuring 8 health domains: Physical functioning, bodily pain, role limitations due to physical problems, role limitations due to emotional problems, general health perceptions, mental health, social function, and vitality. The participant's responses are solicited using Likert scales that vary in length, with 3 to 6 response options per item. The SF-36 will be scored using 2 overall summary scores: Physical component summary and mental component summary scores. A higher score indicates better health status. Details about scoring rules and derivations of domain scores can be found in Section 9.2.3
- Patient Global Impression of Change (PGIC). It is the PRO counterpart to the Clinical Global Impressions (CGI) scale, which was published in 1976 by the National Institute of Mental Health (US). It consists of one item taken from the CGI and adapted to the patient.
- UC-related hospitalizations.
- UC-related surgeries, including colectomy.

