5.2.2. Analyses for Continuous Non-Cardiac Endpoints

All continuous exploratory efficacy endpoints, HRQoL endpoints and efficacy-related biomarker endpoints measured longitudinally will be summarized by visit using descriptive statistics (n, mean, standard deviation [SD], median, minimum, and maximum), and presented in a listing. They will also be analyzed using a linear mixed-effect model, with factors for naïve to biologic or JAK inhibitor therapy at study entry (yes or no), baseline corticosteroid use (yes or no), treatment, visit, treatment by visit interaction and baseline value. Reported strata will be used in the model. Unstructured covariance will be used. If there is a convergence issue in fitting the unstructured covariance, other covariance structures, such as a compound symmetry covariance structure will be considered as appropriate. LSM for each treatment group, standard errors (SEs), LSMs in treatment difference and associated 95% CIs, and p-values by visit will be reported.

Analyses above based on linear mixed-effect model may be repeated using actual strata if mis-classification occurs in more than 10% of randomized participants. i.e., if there are more than 10% of randomized participants whose reported strata are not the same as actual strata.

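### SAP Table 7 sends all of Section 3.4.2 to the longitudinal mixed model, leaving UC-related hospitalizations and surgeries without a workable analysis and the PGIC with an unclear one

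*SAP*

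**What the plan says.** SAP 3.4.2 lists the questionnaires, with the PGIC among those reported as scores and change from baseline. It then adds two separate bullets: UC-related hospitalizations and "UC-related surgeries, including colectomy". Protocol 10.10.2 gives the type of both event endpoints. They are proportions of subjects, for example "The proportion of subjects requiring UC-related surgeries, including colectomy".

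SAP 6.1 states that the analyses of the Section 3.4.2 endpoints are those in Tables 6 and 7. Only Table 7 covers them, in the single row "HRQoL endpoints (Section 3.4.2". The entry for both main analysis and missing-data handling is "Same as continuous exploratory efficacy endpoint". That points to the model of Section 5.2.2 on the Primary Analysis Set, without explicit imputation and assuming data missing at random. Section 5.2.2 says: "They will also be analyzed using a linear mixed-effect model, with factors for naïve to biologic or JAK inhibitor therapy at study entry". The remaining terms are baseline corticosteroid use, treatment, visit, treatment by visit, and baseline value.

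Estimand 2 (SAP 2.2.4) also cites Section 3.4.2. Its intercurrent events are treatment discontinuation for any reason, rescue medication, a dose increase in existing UC medication, and a fourth: "Have a rescue non-drug treatment (eg, colectomy, ileostomy, or sigmoidectomy) during the study". For participants with any of these, "their data collected up to the intercurrent events will be used for analysis".

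In the protocol's Schedule of Assessments (Table 6), the questionnaire row ending "FACIT-F, urgency NRS, and PGIC" is marked at Week 0/Day 1.

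**The concern.** Hospitalization and surgery for UC matter a great deal to patients, and the protocol promises a proportion for each. The only analysis the SAP assigns to them is built for a score measured repeatedly with a baseline value. A programmer following Table 7 would have to improvise: choose a denominator, decide how long to count, decide whether events after stopping study drug count, and choose a treatment comparison. With few expected events, those choices could visibly change the reported percentages, and they should not be made after unblinding.

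The PGIC raises a smaller question. It asks the participant to rate change, so subtracting a Day 1 rating from a later one gives a quantity with no plain reading.

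**Working it through.** The plan has no figure to reproduce here. The check is mainly a comparison of sections.

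**1. Does the assigned model fit the event endpoints?** The model of 5.2.2 needs a value at each visit, a baseline value and a treatment-by-visit term, and reports least-squares means by visit. A participant either has or has not had a UC surgery by the end of observation: one 0/1 outcome, no baseline, no visit series. The model does not estimate the protocol's proportion. Nor is the row simply shorthand. In the same table Section 3.4.1 is split into binary and continuous rows, and lymphocyte counts get an exception to the analysis set. Section 3.4.2 gets neither.

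**2. Is a method given elsewhere?**
- Estimand 1 (2.2.3) covers Sections 3.1, 3.2.1 and 3.4.1 only.
- Section 5.2.1 covers binary efficacy endpoints.
- Section 5.2 says that binary variables are shown as number and percent. It gives no window, no intercurrent-event rule and no comparison.
- Table 12 gives date rules for hospitalization, so a variable is evidently to be derived, but no analysis uses it.
- Section 6.3.1.5 compares serious TEAEs, which is not specific to UC. Protocol 9.9.9.2.2 also records the illness and not the surgical procedure as the SAE, so those tables do not yield a surgery count.
- Section 9.3 does not classify exposure in the follow-up period as rescue therapy, so the rescue listing does not yield a full surgery count either.

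**3. What would Estimand 2 do?** There are two readings.
- *Literal Table 7 plus 2.2.4:* data count only up to an intercurrent event, so a hospitalization or surgery after discontinuation, or after another intercurrent event, is dropped.
- *Narrow wording:* the variable in 2.2.4 is limited to continuous variables, and 5.2.2 and 5.3.2 to endpoints measured longitudinally. The two event endpoints then have no estimand and no model.

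Both readings lead to the same repair.

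**4. Size.** The planned primary-set numbers are 122 etrasimod and 61 placebo (SAP 2.3). One event is 1/122 = 0.8 percentage points or 1/61 = 1.6 points. The documents give no event rate, so a range of 1% to 5%, equal in both arms, is assumed. Expected participants with an event = n × p; chance of no placebo event = (1 − p)^61.

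| Assumed p | Etrasimod, 122p | Placebo, 61p | Chance of no placebo event |
|---|---|---|---|
| 1% | 1.2 | 0.6 | 54% |
| 3% | 3.7 | 1.8 | 16% |
| 5% | 6.1 | 3.1 | 4% |

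The outcomes would be sparse across this range.

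**5. PGIC.** Let Y be the post-baseline score, B the Day 1 value and T treatment. If Y − B = a + bT + cB + other terms, then Y = a + bT + (c + 1)B + the same other terms. The treatment coefficient b is identical. What differs is the arm-level mean, which is shifted by the mean of B, and the descriptive change summaries. A participant without a Day 1 value would also leave the model.

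**The case against.** The strongest reply is that the plan can be read sensibly. Sections 5.2.2 and 5.3.2 concern continuous longitudinal endpoints, the protocol calls the two events proportions, the SAP's list of modifications does not alter that, and Section 5.2 already provides number and percent for binary variables. On that view a descriptive proportion is the natural output, and Table 7 is only loosely worded. This stands in part: a count and percent is a reasonable default. It does not remove the conflict with Section 6.1, which points to Table 7 for the analysis, and it settles neither the window nor the handling of events after discontinuation.

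A reader might go further and infer that the SAP's estimand stops counting at the very surgery or discontinuation that these endpoints should capture. The documents do not support that:
- Table 7 names no estimand, and 2.2.4 is limited to continuous variables.
- Discontinuation is not an event these endpoints count.
- Hospitalization is not an intercurrent event.
- The SAP does not say that a surgery marking the cut-off goes uncounted.

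Nor does the SAP apply nonresponder imputation here, since 5.3.1 concerns binary efficacy endpoints. Nothing in the documents shows that placebo would lose more events.

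On the PGIC, both documents openly list change from baseline, a Day 1 assessment is scheduled, and 5.2.2 does not name the dependent variable. The objection is therefore to how the change summaries can be interpreted; the treatment comparison is not at fault.

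**Conclusion.** The point holds as a specification error with limited reach. As written, Table 7 assigns two binary event endpoints a model that cannot estimate what the protocol asks for, and only a generic descriptive rule stands behind it. Loss of events after discontinuation follows only if Table 7 and Estimand 2 are applied literally to endpoints that the narrower wording of 2.2.4, 5.2.2 and 5.3.2 leaves out. The PGIC issue affects arm-level and descriptive summaries only.

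No endpoint in the fixed testing sequence of SAP 5.1 is touched. Event counts are unknown and probably small; the illustration above rests on an assumed 1% to 5% rate. The amount recoverable after discontinuation is also modest. Protocol 9.5 provides follow-up visits at 2 and 4 weeks after the last dose, and only for those who do not enter the open-label extension.

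**What to change.** Split the Section 3.4.2 row of Table 7.

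- **UC-related hospitalizations and surgeries:** n (%) of participants with at least one event from first dose to last study visit, counted regardless of intercurrent events and without nonresponder imputation. State the analysis set; the Primary Analysis Set is the Section 6.1 default. For the comparison, use the unstratified Wilson risk difference or the exposure-adjusted rate difference already in Section 6.3.1.5. Show exposure alongside, because follow-up after discontinuation is short and extension entrants have no follow-up visits. The four-stratum MH method of 5.2.1 suits so few events poorly.
- **PGIC:** analyse the Week 12 and Week 52 score itself, with no baseline value and no change from baseline.
- **Other scales:** keep the mixed model. Reword 5.3.2 so that it no longer describes all HRQoL endpoints as continuous.

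The cost is one table edit and a few simple outputs. Protocol 6.7 already requires procedures to be recorded in the eCRF through the safety reporting period, and hospitalizations are captured through SAE reporting. The remaining limitation is unequal and short observation after stopping study drug, which showing exposure makes visible but does not remove.
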